5.5.11. Quality-of-Life (QoL) Analyses

The mean change from baseline to each postbaseline visit for SP III and SP III/IV/V for MSQ (including Role Function-Restrictive, Role Function-Preventive, Emotional Function, and total score), as defined in Section 5.4.3 will be evaluated using MMRM as described in Section 5.5.10.1.

Mean change from baseline to LOCF endpoint in the 3-month treatment phase for above quality of life measures will be evaluated using the ANCOVA model as described in Section 5.5.1.1.

The change from baseline to Month 3 score in MIDAS (item scores and total score) will be evaluated using the ANCOVA model as described in Section 5.5.1.1. The mean change from baseline to each postbaseline visit for SP III/IV and for SP III/IV/V for MIDAS (item scores and total score) will be evaluated using MMRM as described in Section 5.5.10.1.

Indicators of the MSQ Role Function Restrictive domain responders and MIDAS responders will be analyzed using GLIMMIX (as described in Section 5.5.10.3). Threshold for MSQ Role Function Restrictive domain response will be derived as outlined in "Statistical Analysis Plan for Psychometric Properties of the MSQv2.1 Role Function-Restrictive Domain". The threshold for MIDAS response will be a 50% improvement from baseline in MIDAS total score.

For the HCRU, the following measures will be analyzed:

- number of hospital emergency room (ER) visits
- number of overnight hospital stays
- number of other visits with healthcare professional
- number of hospital ER visits related to migraine headache
- number of overnight hospital stays related to migraine headache
- number of other visits with healthcare professional related to migraine headache

All of the above measures for the HCRU will be analyzed with a repeated measures negative binomial regression analysis fitted with SAS PROC GLIMMIX. The model includes pooled country, month, baseline medication overuse (yes versus no), concurrent prophylaxis use (yes versus no) and treatment-by-month interaction, as well as the continuous fixed covariates of

baseline and baseline-by-month interaction, log (number of actual number of days within every 3 month/90) as the offset in the model. In case of non-convergence, pooled country and/or baseline-by-month interaction may not be included in the model.

Employment status at each visit will be summarized separately for each treatment groups.

5.5.12. Safety Analyses

The safety analyses will be conducted for SP III, SP IV, SP V, SP III/IV, and SP III/IV/V.

Unless specified otherwise, for SP III, SP IV, SP V, and SP III/IV separately, the safety analyses outlined in the following sub-sections will be conducted; for SP III/IV/V, only the change from baseline with MMRM analysis and time to event analysis will be conducted.

The safety and tolerability of treatment will be assessed by summarizing the following:

- TEAEs
 - o By PT
 - o By SOC
 - o By maximum severity
 - o By considered to be related to investigational produce by investigator
- SAEs
- AE leading to discontinuation
- Suicide-Related Thoughts and Behaviors
- Vital signs and weight
- Laboratory measurements
- ECGs
- Antibodies (ADA and NAb)

The baseline and postbaseline for all safety measures are described in Table CGAI.5.4 unless specified otherwise.

5.5.12.1. Categorical Safety Variables

Unless specified otherwise, the categorical safety analyses will include both scheduled and unscheduled visits. Categorical safety analyses will only be conducted for SP III, SP IV, SP V, and SP III/IV separately.

Comparisons between treatment groups for all categorical safety measures will be made using CMH test for SP III, and SP III/IV with the ITT population.

Descriptive statistics only will be presented for the treatment groups in SP IV and SP V.

5.5.12.1.1. Adverse Events

Treatment-emergent AEs are defined as the reported AEs that first occurred or worsened during the postbaseline phase compared with baseline phase. For each TEAE, the severity level of the event (mild, moderate, or severe) will be determined by patient or physician opinion. The MedDRA Lowest Level Term (LLT) will be used in the treatment-emergent computation. For each LLT, the maximum severity at baseline will be used as the baseline severity. If the maximum severity during postbaseline is greater than the maximum baseline severity, the event is considered to be treatment-emergent for the specific postbaseline period. For each patient and TEAE, the maximum severity for the MedDRA level being displayed (PT, High Level Term, or SOC) is the maximum postbaseline severity observed from all associated LLTs mapping to that MedDRA level. For events that are gender-specific, the denominator and computation of the percentage will include only patients from the specific gender.

5.5.12.1.1.1. Potential Hypersensitivity Events

Potential hypersensitivity events (immediate and non-immediate) will be identified from a review of preferred terms generated from the following queries:

- Anaphylactic reaction (SMQ 20000021)
- Broad and narrow terms in the Angioedema (SMQ 20000024)
- Broad and narrow terms in the Hypersensitivity (SMQ 20000214)

A listing of patients having an event identified from these analyses will be medically reviewed to determine if the terms identified represent actual hypersensitivity events. Listings should include information on timing of event relative to latest dose of study drug administration, the event term from this query, other AEs for the patient and timing, any abnormal laboratory findings, medical history and anti-drug antibody test results including titer. Only those that are judged medically to be hypersensitivity events will be included in the final tables.

The number and percentage of patients with TEAEs, SAEs, and AEs resulting in study drug discontinuation will be summarized by treatment groups using MedDRA PT nested within the SMQ. Events will be ordered by decreasing frequency within the SMQ.

The number and percentage of patients with treatment-emergent hypersensitivity events by maximum severity will be summarized by treatment groups using MedDRA PT.

The number and percentage of patients with TE hypersensitivity events by timing will be summarized using MedDRA PT. Events will be ordered by decreasing frequency. Note the timing of the hypersensitivity events is collected through eCRF and categorized into the following 4 categories:

- Immediate occurs within minutes (<60 minutes) from study drug administration.
- Acute Reaction occurs from 1 up to 6 hours from study drug administration.

- Delayed Reaction occurs from >6 hours through 14 days from study drug administration, which will be split into 2 categories: on the same day of injection and after the day of injection.
- Reaction >14 days from study drug administration.

The relationship between the development of TEAE of hypersensitivity events and treatment-emergent ADA within LY2951742 dose groups will be examined.

5.5.12.1.1.2. Adverse Events Related to Injection Sites

Adverse events related to injection sites will be defined using terms from the MedDRA High Level Term "Injection Site Reactions".

The number and percentage of patients with TEAEs related to injection sites, SAEs related to injection sites, and AEs related to injection sites resulting in study drug discontinuation will be summarized using MedDRA PT nested within the High Level Term. Events will be ordered by decreasing frequency within High Level Term.

The number and percentage of patients with TEAEs related to injection sites by maximum severity will be summarized by treatment groups using MedDRA PT nested within the High Level Term. For each patient and AE related to injection sites, the maximum severity for the MedDRA level being displayed (PT) is the maximum postbaseline severity observed from all associated LLTs mapping to that MedDRA level.

The number and percentage of patients with TEAEs related to injection sites by timing will be summarized using MedDRA preferred terms ordered by decreasing frequency. Note the timing of AEs related to injection sites is collected through eCRF and categorized into the same categories as for hypersensitivity events.

The relationship between the development of TEAEs related to injection sites and TE hypersensitivity events will be examined for all treatment groups. Additionally, the relationship between the development of TEAEs related to injection sites and treatment-emergent ADA will be examined for LY2951742 group.

5.5.12.1.1.3. Upper Respiratory Tract Infections

Upper respiratory tract infections will be defined using all the PTs from the 2 high level terms of "upper respiratory tract infections" and "upper respiratory tract infections NEC" as defined in MedDRA.

The number and percentage of patients with TEAEs of upper respiratory tract infections will be summarized by treatment group using MedDRA PTs. Events will be ordered by decreasing frequency in the pooled LY2951742 group.

The number and percentage of patients with TEAEs of upper respiratory tract infections by maximum severity will be summarized by treatment groups using MedDRA PT. For each patient and upper respiratory tract infection event, the maximum severity for the MedDRA level being displayed (PT) is the maximum postbaseline severity observed from all associated LLTs mapping to that MedDRA level.

By-subject listings of treatment-emergent upper respiratory tract infections, and upper respiratory tract infections leading to study drug discontinuation will be provided.

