8.2. Adverse Events

Investigators are responsible for monitoring the safety of patients who have entered this study and for alerting Lilly or its designee to any event that seems unusual, even if this event may be considered an unanticipated benefit to the patient.

The investigator is responsible for the appropriate medical care of patients during the study.

Investigators must document their review of each laboratory safety report.

The investigator remains responsible for following, through an appropriate health care option, AEs that are serious or otherwise medically important, considered related to the investigational product or the study, or that caused the patient to discontinue the investigational product before completing the study. The patient should be followed until the event resolves, stabilizes with appropriate diagnostic evaluation, or is reasonably explained. The frequency of follow-up evaluations of the AE is left to the discretion of the investigator.

Lack of drug effect is not an AE in clinical studies, because the purpose of the clinical study is to establish treatment effect.

After the ICF is signed, study site personnel will record via eCRF the occurrence and nature of each patient's pre-existing condition(s), including clinically significant signs and symptoms of the disease under treatment in the study. In addition, site personnel will record via eCRF any change in the condition(s) and any new condition(s) as AEs. Investigators should record their assessment of the potential relatedness of each AE to protocol procedure or investigational product via eCRF.

The investigator will decide whether he or she interprets the observed AEs as reasonably possibly related to migraine headache, to the investigational product, study device, study procedure, or other concomitant treatment or pathologies.

The investigator will answer yes/no when making this assessment.

Planned surgeries and nonsurgical interventions should not be reported as AEs unless the underlying medical condition has worsened during the course of the study.

If a patient's investigational product is discontinued as a result of an AE, study site personnel must report this to Lilly or its designee via eCRF, clarifying if possible, the circumstances leading to discontinuations of treatment.

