9.5.2. Adverse Events

Treatment-emergent adverse events are defined as the reported AEs that first occurred or worsened during the postbaseline phase compared with baseline phase. For each TEAE, the severity level of the event (mild, moderate, or severe) will be determined by patient or physician opinion. The Medical Dictionary for Regulatory Activities (MedDRA) Lowest Level Term will be used in the treatment-emergent computation. For each Lowest Level Term, the maximum severity at baseline will be used as the baseline severity. If the maximum severity during postbaseline is greater than the maximum baseline severity, the event is considered to be treatment-emergent for the specific postbaseline period. For each patient and TEAE, the maximum severity for the MedDRA level being displayed (Preferred Term, High Level Term, or SOC) is the maximum postbaseline severity observed from all associated Lowest Level Terms mapping to that MedDRA level.

For events that are gender-specific, the denominator and computation of the percentage will include only patients from the given gender.

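### The TEAE severity rule does not limit the maximum to treatment-emergent LLTs, so a mild TEAE can be tabulated at a higher severity that neither began nor worsened in that period

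*SAP*

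**What the plan says.** SAP 5.5.12.1.1 sets out the adverse event rules in sequence.

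- Definition: "Treatment-emergent AEs are defined as the reported AEs that first occurred or worsened during the postbaseline phase compared with baseline phase".
- Level of the test: "The MedDRA Lowest Level Term (LLT) will be used in the treatment-emergent computation".
- The test itself: "If the maximum severity during postbaseline is greater than the maximum baseline severity, the event is considered to be treatment-emergent", judged for the particular postbaseline period.
- Severity in the tables: the sentence opens "For each patient and TEAE, the maximum severity for the MedDRA level being displayed" and continues "PT, High Level Term, or SOC) is the maximum postbaseline severity observed from all associated LLTs mapping to that MedDRA level".

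Protocol 9.5.2 has the same rule with LLT spelled out: the displayed severity "is the maximum postbaseline severity observed from all associated Lowest Level Terms mapping to that MedDRA level". SAP 5.5.12.1.1.2 (injection sites) and 5.5.12.1.1.3 (upper respiratory tract infections) repeat it for display by PT.

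Three other places bear on the point.

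- Protocol 8.2 has sites record pre-existing conditions after consent, "including clinically significant signs and symptoms of the disease under treatment in the study", and then record as AEs any change in those conditions and any new condition.
- SAP Table CGAI.5.4 sets the TEAE baseline at all of Visits 1–3 for Study Period (SP) III, Visits 1–7 for SP IV and Visits 1–16 for SP V.
- SAP 5.5.12 lists TEAEs by maximum severity among the planned safety summaries.

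**The concern.** The emergence test and the severity rule work on different sets of LLTs. The test asks, for each LLT, whether the patient got worse. The severity rule takes the highest postbaseline severity among the LLTs that map to the displayed term, and the only stated condition is that they map there. An LLT that failed the emergence test can therefore supply the severity printed against a different LLT that passed it.

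That conflicts with the plan's own definition of a TEAE as something that first occurred or worsened. A table of TEAEs by maximum severity is normally read as showing how severe the emergent events were. Under the literal rule, some of the moderate or severe entries could describe background illness or events carried over from an earlier period. The text also leaves room for two programmers to follow it faithfully and produce different tables.

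**Working it through.** The plan states no figure for this point, so there is nothing to reproduce. The check runs the rule as logic and then illustrates its size.

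**Step 1: code the rule.** Severity is 0 none, 1 mild, 2 moderate, 3 severe. An LLT is emergent if its postbaseline severity exceeds its baseline severity (SAP 5.5.12.1.1). Two readings of the displayed severity are compared:

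- literal: maximum postbaseline severity over all LLTs under the displayed term;
- restricted: the same maximum over emergent LLTs only.

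**Step 2: worked cases.** LLT A goes from none to mild (emergent). LLT B lies under the same displayed term.

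| LLT B, baseline to postbaseline | B emergent? | Literal | Restricted |
|---|---|---|---|
| severe to severe | no | severe | mild |
| severe to moderate | no | moderate | mild |
| severe, with no postbaseline severity record | no | mild | mild |

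**Step 3: all patterns for two LLTs.** There are 4 × 4 × 4 × 4 = 256 patterns.

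- For one LLT, 6 of the 16 baseline/postbaseline pairs are emergent and 10 are not. Patterns with at least one emergent LLT: 256 − 10 × 10 = 156.
- The readings differ when a non-emergent LLT has a higher postbaseline severity than the emergent one.
- Emergent LLT ending mild (1 pair) with a non-emergent LLT of moderate to moderate, severe to moderate or severe to severe (3 pairs): 1 × 3 = 3.
- Emergent LLT ending moderate (2 pairs) with severe to severe (1 pair): 2 × 1 = 2.
- Either LLT can be the emergent one: 2 × (3 + 2) = 10 patterns.

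The literal reading is higher in all 10. In 8 the higher value comes from an unchanged LLT, and in 2 from one that improved from severe to moderate. These are counts of logical patterns, not expected frequencies.

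**Step 4: can the documents produce such data?**

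- *Improved condition.* Protocol 8.2 has any change in a pre-existing condition recorded as an AE. Severe improving to moderate is a change. It is not emergent, yet it outranks a new mild event.
- *Event carried from SP III into SP IV.* With Visits 1–7 as the SP IV baseline, a severe AE that began in SP III and continues at the same severity is not emergent in SP IV. It is already in the AE data. If its severity is counted in SP IV, it can raise a new mild SP IV event under the same term to severe.
- *Unchanged pre-existing condition.* This works only if the condition carries a postbaseline severity, and the documents do not say whether it does.

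**Step 5: illustrative size.** Patients moved up = n × q × b, where q is the share with a non-severe TEAE in one SOC and b is the share who independently carry an unchanged severe condition in that SOC with a postbaseline record. The planned n is 285 per LY2951742 arm and 570 on placebo (SAP 5.2). The values of q and b are assumptions that are not in the documents.

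| q | b | per 285 | per 570 |
|---|---|---|---|
| 10% | 1% | 0.3 | 0.6 |
| 20% | 5% | 2.9 | 5.7 |
| 30% | 10% | 8.6 | 17.1 |

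**The case against.** The strongest reply is that the severity sentence is about TEAEs from its first words, "For each patient and TEAE, the maximum severity for the MedDRA level being displayed". On that view the associated LLTs are those that make up the TEAE, and non-emergent LLTs never enter. This is a fair reading and the sponsor may already program it that way. But the opening words say which patient-events receive a severity, whereas the later words say where the severity is taken from, and there the only stated condition is mapping to the displayed level. The sentence does not settle the matter.

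A reader might also infer something stronger: that unchanged severe pre-existing conditions will be common in chronic migraine, and so the severity tables will certainly be inflated. The documents do not support that. Protocol 8.2 shows that pre-existing conditions, including signs and symptoms of the study disease, are recorded at the outset. It then asks for changes and new conditions to be recorded as AEs, and says nothing about a postbaseline severity for a condition that stays the same. Without that record the literal rule also shows mild. The exclusions in Protocol 5.2 for serious cardiovascular risk, unstable psychiatric disease and illness judged to preclude participation also argue against assuming a large share of such patients.

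The reach is limited too. SAP 5.5.12 lists the summaries by PT, by SOC and by maximum severity as separate items and does not fix the level of the general severity table. The severity tables whose level is stated (hypersensitivity, injection site and upper respiratory tract infection) are by PT, where few LLTs share a term. A severe injection-site reaction present before the first study injection is implausible. All of this stands, and it limits the size of the point. It does not remove the improved-condition and SP III-to-SP IV routes.

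**Conclusion.** The concern holds as a gap in the rule. As written, a mild TEAE can be displayed at a higher severity because of a non-emergent LLT under the same term, contrary to the plan's definition of treatment emergence. This is a possibility under the literal reading, not a demonstrated error in any output.

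The consequence is confined to severity grading. It does not change who is counted with a TEAE, an SAE or a discontinuation due to an AE. It touches every arm, matters mainly if severity is shown by SOC or HLT, and is small by PT. For SP IV and SP V, SAP 5.5.12.1 plans descriptive statistics only, so the carry-over route for SP IV alone affects a descriptive table.

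How often it would happen cannot be determined from the documents. The range of 0.3 to 8.6 of 285 patients and 0.6 to 17.1 of 570 rests on assumed shares, on independence between them, and on a postbaseline severity record existing for the non-emergent condition.

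**What to change.** In SAP 5.5.12.1.1, replace *all associated LLTs* with *all associated treatment-emergent LLTs*. Use the same wording in 5.5.12.1.1.2 and 5.5.12.1.1.3; the effect there is slight, but the three sentences should agree. Because 5.5.12.1.1 already judges emergence for the specific postbaseline period, the new wording also keeps SP III events that have not worsened out of the SP IV severity grades.

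The cost is one added term in three sentences and a filter in the severity program, with no new data. If the program already works this way, the edit only documents it. The SAP states in its revision history that it supersedes the statistical plans in the protocol, and SAP 5.5.1 calls for an amendment only when a principal feature changes, so Protocol 9.5.2 need not be amended for this.

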5.5.12.1.2. Suicide-Related Thoughts and Behaviors

Suicidal ideation, suicidal behavior, and self-injurious behavior without suicidal intent occurring during treatment, based on the C-SSRS, will be summarized by treatment. In particular, for each of the following events, the number and percent of patients with the event will be enumerated by treatment: completed suicide, nonfatal suicide attempt, interrupted attempt, aborted attempt, preparatory acts or behavior, active suicidal ideation with specific plan and intent, active suicidal ideation with some intent to act without specific plan, active suicidal ideation with any methods (no plan) without intent to act, nonspecific active suicidal thoughts, wish to be dead, and self-injurious behavior without suicidal intent.

In addition, the number and percent of patients who experienced at least 1 of various composite measures will be presented and compared. These include suicidal behavior (completed suicide, non-fatal suicidal attempts, interrupted attempts, aborted attempts, and preparatory acts or behavior), suicidal ideation (active suicidal ideation with specific plan and intent, active suicidal ideation with some intent to act without specific plan, active suicidal ideation with any methods [no plan] without intent to act, non-specific active suicidal thoughts, and wish to be dead), and suicidal ideation or behavior.

The number and percent of patients who experienced at least 1 of various comparative measures during treatment will be summarized and compared for SP III, and summarized for SP IV and SP V. These include treatment-emergent suicidal ideation compared to recent history, treatment-emergent serious suicidal ideation compared to recent history, emergence of serious suicidal ideation compared to recent history, improvement in suicidal ideation at endpoint compared to baseline, and emergence of suicidal behavior compared to all prior history.

Specifically, the following outcomes are C-SSRS categories and have binary responses (yes/no). The categories have been re-ordered from the actual scale to facilitate the definitions of the composite and comparative endpoints, and to enable clarity in the presentation of the results.

Category 1 – Wish to be Dead

Category 2 – Non-specific Active Suicidal Thoughts

Category 3 – Active Suicidal Ideation with Any Methods (Not Plan) without Intent to Act

Category 4 – Active Suicidal Ideation with Some Intent to Act, without Specific Plan

Category 5 – Active Suicidal Ideation with Specific Plan and Intent

Category 6 – Preparatory Acts or Behavior

Category 7 – Aborted Attempt

Category 8 – Interrupted Attempt

Category 9 – Actual Attempt (non-fatal)

Category 10 – Completed Suicide

Self-injurious behavior without suicidal intent is also a C-SSRS outcome (although not suicide-related) and has a binary response (yes/no).

Composite endpoints based on the above categories are defined below.

- Suicidal ideation: A "yes" answer at any time during treatment to any 1 of the 5 suicidal ideation questions (Categories 1-5) on the C-SSRS.
- Suicidal behavior: A "yes" answer at any time during treatment to any 1 of the 5 suicidal behavior questions (Categories 6-10) on the C-SSRS.
- Suicidal ideation or behavior: A "yes" answer at any time during treatment to any 1 of the ten suicidal ideation and behavior questions (Categories 1-10) on the C-SSRS.

The following outcome is a numerical score derived from the C-SSRS categories. The score is created at each assessment for each patient and is used for determining treatment emergence.

• Suicidal Ideation Score: The maximum suicidal ideation category (1-5 on the C-SSRS) present at the assessment. A score of 0 is assigned if no ideation is present.

For SP III, SP IV and SP V, comparative endpoints of interest are defined below. "Treatment emergence" is used for outcomes that include events that first emerge or worsen. "Emergence" is used for outcomes that include events that first emerge.

Treatment-emergent suicidal ideation compared to recent history:

- An increase in the maximum suicidal ideation score during treatment (Visit 3.01 to Visit 7 for SP III; Visit 7.01 to Visit 16 for SP IV; Visit 16.01 to Visit 18 for SP V) from the maximum suicidal ideation category during the screening and lead-in periods (C-SSRS scales taken at Visits 1 to 3 excluding "lifetime" for SP III; C-SSRS scales taken at Visit 1 to Visit 7 excluding "lifetime" for SP IV; C-SSRS scales taken at Visit 1 to Visit 16 excluding "lifetime" for SP V).
- Treatment-emergent serious suicidal ideation compared to recent history: An increase in the maximum suicidal ideation score to 4 or 5 on the C-SSRS during treatment (Visit 3.01 to Visit 7 for SP III; Visit 7.01 to Visit 16 for SP IV; Visit 16.01 to Visit 18 for SP V) from not having serious suicidal ideation (scores of 0-3) during the screening and lead-in periods (C-SSRS scales taken at Visit 1 to Visit 3 excluding "lifetime" for SP III; C-SSRS scales taken at Visit 1 to Visit 7 excluding "lifetime" for SP IV; C-SSRS scales taken at Visit 1 to Visit 16 excluding "lifetime" for SP V).

Emergence of serious suicidal ideation compared to recent history:

• An increase in the maximum suicidal ideation score to 4 or 5 on the C-SSRS during treatment (Visit 3.01 to Visit 7 for SP III; Visit 7.01 to Visit 16 for SP IV; Visit 16.01 to Visit 18 for SP V) from no suicidal ideation (scores of 0) during the screening and lead-in periods (C-SSRS scales taken at Visit 1 to Visit 3 excluding "lifetime" for SP III; C-SSRS scales taken at Visit 1 to Visit 7 excluding "lifetime" for SP IV; C-SSRS scales taken at Visit 1 to Visit 16 excluding "lifetime" for SP V). Recent history excludes "lifetime" scores from the Baseline C-SSRS scale or Baseline/Screening C-SSRS scale.

Improvement in suicidal ideation at endpoint compared to baseline:

• A decrease in suicidal ideation score at endpoint (the last measurement during Visit 3.01 to Visit 7 for SP III; the last measurement during Visit 7.01 to Visit 16 for SP IV; the last measurement during Visit 16.01 to Visit 18 for SP V) from the baseline measurement (the measurement taken just prior to treatment (Visit 3 for SP III; the last non-missing measure during Visit 3.01 to Visit 7 for SP IV; the last non-missing measure during Visit 7.01 to Visit 16 for SP V).

Emergence of suicidal behavior compared to all prior history:

• The occurrence of suicidal behavior (Categories 6-10) during treatment (Visit 3.01 to Visit 7 for SP III; Visit 7.01 to Visit 16 for SP IV; Visit 16.01 to Visit 18 for SP V) from not having suicidal behavior (Categories 6-10) prior to treatment (Visit 1 to Visit 3 including "lifetime" for SP III; C-SSRS scales taken at Visit 1 to Visit 7 including "lifetime" for SP IV; C-SSRS scales taken at Visit 1 to Visit 16 including "lifetime" for SP V).

The same comparative endpoints of interest will also be analyzed for SP IV and SP V (refer to Table CGAI.5.4 for a definition of baseline and postbaseline visits).

Patients who discontinued from the study with no postbaseline C-SSRS value will be considered unevaluable for analyses of suicide-related events. Only evaluable patients will be considered in the analyses. The CMH test will be used for treatment comparisons. For each event, p-values will only be displayed if at least 4 events occurred in at least 1 treatment group.

